3. AMENDMENTS AND UPDATES

Number	Date	Section of study protocol	Amendment or update	Reason
1				
2				

4. MILESTONES

Milestone	Planned Date
Start of data extract	AUG 2023
End of data analysis	DEC 2023
Final report of study results	FEB 2024

5. RATIONALE AND BACKGROUND

Interstitial lung disease (ILD) is a broad term that describes more than 200 diverse lung disorders, including idiopathic pulmonary fibrosis (IPF), autoimmune ILD, hypersensitivity pneumonitis (HP), and sarcoidosis.¹ Typical symptoms of ILD include cough and dyspnea, as well as decreased lung capacity², which leads to exercise intolerance and hypoxemia.

The major goal of therapy in ILD patients is to slow disease progression as well as improve the associated dyspnea, exercise capacity, and health-related quality of life.³ Approved treatment options for fibrosing ILD comprise antifibrotic treatments including nintedanib and pirfenidone, which slow the rate of decline in forced vital capacity (FVC). Other commonly prescribed treatment options are corticosteroids, immunosuppressants, opioids, and lung transplantation.⁴ Despite advances in pharmacotherapy, many patients continue with disease progression. Oxygen therapy is commonly administered to reduce breathlessness and increase physical capacity by improving gas exchange.⁵

Supplemental oxygen (O₂) is commonly prescribed in clinical practice for patients with fibrotic ILD; however, robust evidence to support its long-term use is lacking. Recommendations for long-term oxygen therapy (LTOT) for resting hypoxemia in ILD are largely extrapolated from trials conducted in chronic obstructive pulmonary disease (COPD), where a survival benefit is well established.^{6,7} The American Association for Respiratory Care guideline recommends the use of oxygen therapy to maintain the oxygen saturation (SpO₂) range of 94–98% for most hospitalized patients.⁸ Despite its frequent use, there is a paucity of studies evaluating the incidence, prevalence, and impact of LTOT on outcomes such as disease progression or mortality in ILD. This study will help fill in the gaps in increasing the understanding of the use of oxygen therapy among fibrosing ILD patients and assess whether the use of oxygen leads to better or worse outcomes.

6. RESEARCH QUESTION AND OBJECTIVES

The purpose of this study is to examine oxygen therapy utilization and assess its impact on clinical and economic outcomes of ILD patients. There are three aims for this project:

Aim 1: *To describe initiation and use of oxygen therapy among patients with fibrotic ILD. The specific objectives for Aim 1 are to:*

- Examine the incidence and prevalence of oxygen therapy among patients with fibrotic ILD
- Assess the time to first oxygen therapy among fibrotic ILD patients naïve to oxygen therapy, and examine factors/variables associated with oxygen therapy initiation

Aim 2: *To assess the impact of oxygen therapy on clinical outcomes among patients with fibrotic ILD. The specific objective for Aim 2 is to:*

- Evaluate the impact of oxygen therapy initiation on clinical outcomes, including disease progression and mortality, among fibrotic ILD patients

7. RESEARCH METHODS

7.1 STUDY DESIGN

[figure not shown]
This is a non-interventional study of patients enrolled in a commercial, Medicaid, or Medicare plan, using existing administrative claims and EHR data in Optum's Market Clarity Integrated Claims + Clinical database for the period of 01 October 2015 through 30 June 2022 (study period). The study period may be extended through latest data available at the time of study implementation to increase study sample.

To describe the initiation and use of oxygen therapy after first fibrosing ILD diagnosis (**Aim 1**), patients aged ≥ 18 years with newly diagnosed fibrosing ILD will be identified from 01 October 2016 through 30 June 2022 (patient identification period). A schematic of the observation and identification periods is presented in Figure 1. Patients will be required to have 12 months of baseline continuous enrollment prior to fibrosing ILD diagnosis for collecting patient demographics and clinical characteristics. The pre-ILD baseline period will also be used to describe baseline prevalence of oxygen therapy use. Patients will be followed for a variable period from the fibrosing ILD diagnosis date (Section 7.2.2) until the earlier of disenrollment from the health plan, end of study period, or death. Oxygen therapy use will be described, and results will be stratified by underlying cause of fibrosis (e.g., IPF vs non-IPF ILD). Factors associated with initiation of oxygen therapy will be assessed using multivariable methods.

To assess the impact of oxygen therapy use on outcomes (**Aim 2 and Further Aim**), patients with fibrosing ILD who initiated oxygen therapy will be propensity score matched to those who did not yet initiate oxygen therapy. A schematic of the observation and identification periods is presented in Figure 2. The index date will be defined as the date of oxygen therapy initiation for oxygen therapy cohort, or a date that is eligible for index and is similar to the

[figure not shown]
matched case's index date for no oxygen therapy cohort. Disease progression, acute exacerbations, health care resource utilization (HCRU), and health care costs in the Aim 2 follow-up period will be described and compared between matched cohorts. Outcomes will be modelled using multivariable methods.

Figure 1. Observation and Identification Periods: Aim 1

*The ILD diagnosis date will be defined as the first date of a claim with diagnosis for fibrosing ILD during the identification period. Patients will be followed from the fibrosing ILD diagnosis date until the earlier of disenrollment from the health plan, death, or end of the study period. Figure is not to scale and is for illustrative purposes only.

Figure 2. Observation and Identification Periods: Aim 2

*The fibrosing ILD diagnosis date will be before the index date and may be before or during the pre-index baseline period.

†The index date will be defined as the first date of a claim with oxygen therapy (oxygen therapy cohort), or a date that is eligible for index and is similar to the matched case's index date (no oxygen therapy cohort).

Patients will be followed from the index date until the earlier of disenrollment from the health plan, death, or end of the study period.

Figure is not to scale and is for illustrative purposes only.

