7.2 SETTING

7.2.1 Secondary data source selection

The study will use administrative claims and EHR data from Optum's Market Clarity Integrated Claims + Clinical database.

7.2.2 Study population: Aim 1

The analysis for Aim 1 will include patients newly diagnosed with fibrosing ILD during the patient identification period. Patients must meet the following selection criteria to be included in the study:

Inclusion Criteria

- ≥ 2 fibrosing ILD diagnoses in any position on different dates of service, within 365 days of each other, and in the same continuous enrollment period during the patient identification period. The ***fibrosing ILD diagnosis date*** will be defined as the date of the first fibrosing ILD diagnosis. The two fibrosing ILD diagnosis codes can be one of the following combinations:
 - 2 fibrosis codes
 - 1 fibrosis code & 1 ILD code that requires fibrosis code
- ≥ 18 years of age as of the fibrosing ILD diagnosis date
- Continuous enrollment with medical and pharmacy coverage for 12 months prior to the fibrosing ILD diagnosis date (***pre-ILD baseline period***)

Exclusion Criteria

- Fibrosing ILD diagnosis in the 12-month pre-ILD baseline period
- Unknown gender or geographic region

Cohort Assignment

Patients meeting initial selection criteria for Aim 1 will be assigned to cohorts based on known cause of fibrosis:

- **IPF**— ≥ 2 medical claims with diagnosis for IPF in any position during the study period
- **Non-IPF ILD**— < 2 medical claims with diagnosis for IPF during the study period

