7.3.1 Aim 1 Outcomes

7.3.1.1 Primary Outcomes

- **Oxygen Therapy**—Evidence of oxygen use will be captured in the pre-ILD baseline and Aim 1 follow-up periods based on the presence of ≥ 1 diagnosis (ICD-10-CM), procedure (HCPCS, CPT), or revenue code for oxygen therapy. Among patients with oxygen therapy in follow-up, the following aspects of oxygen therapy will be described:
 - **Time to oxygen therapy initiation**—The time in days from the fibrosing ILD diagnosis date to oxygen therapy initiation, among patients without evidence of oxygen therapy in the pre-ILD baseline period.
 - **Sustained oxygen therapy use**—Using claims, sustained oxygen therapy use will be defined among patients with at least 12 months of follow-up after the index date (oxygen initiation date), as a binary variable for the presence of ≥ 11 claims for oxygen therapy in a 12-month period. The following aspects of sustained oxygen therapy will be described:
 - **Time to sustained oxygen therapy use**—The time in days between the index date and the earliest date that defined the sustained oxygen therapy use.
 - **Sustained oxygen therapy use within the first 12 months of follow-up**—The number of patients with the evidence of sustained oxygen therapy use during the first 12 months of follow-up.
 - **Note:** As a sensitivity analysis, sustained oxygen therapy use will also be defined as ≥ 6 claims for oxygen therapy in a 12-month period and, based on the distribution of the count of claims among the population, as the 75th percentile of claims in a 12-month period.

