7.3.5.2 Clinical Characteristics

- **Underlying ILD type**—Patients will be classified into the following underlying ILD types based on claims from the entire study period: autoimmune ILD, HP, sarcoidosis, unclassified ILD/IIP, and multiple. The underlying ILD type will be defined based on the presence of ≥ 1 specific ICD-10-CM diagnosis code for autoimmune ILD, HP, and sarcoidosis. Patients without any underlying ILD diagnosis will be classified into the unclassified ILD/IIP type. Patients with diagnoses for >1 underlying ILD types will be classified as multiple.
- **Respiratory diseases**—Separate indicator variables will be created for the presence of ≥ 1 diagnosis code in any position on a medical claim. The following conditions will be included: pulmonary hypertension, acute respiratory failure, asthma, COPD, pneumonia, lung transplantation, upper respiratory tract infection, lower respiratory tract infection, lung cancer, and cystic fibrosis.
- **Other clinical characteristics** – Similar to respiratory disease, a separate indicator variables will be created for the presence of ≥ 1 diagnosis code in any position on a medical claim. The following conditions will be included: gastroesophageal reflux disease (GERD), heart failure, and obstructive sleep apnea.
- **Quan-Charlson comorbidity score**—A comorbidity score will be calculated based on the presence of diagnosis codes on medical claims.^{10, 11} The Quan-Charlson comorbidity score will also be categorized into the following groups: zero, one to two, three to four, and five or more.
- **Comorbid conditions**—General comorbid conditions will be defined using the Clinical Classifications Software managed by the Agency for Healthcare Research and Quality (AHRQ).¹² This measure generates indicator variables for specific disease

conditions based on ICD-9-CM and ICD-10-CM diagnoses. The top 20 comorbid conditions will be presented.

[figure not shown]
- **Smoking**—An indicator variable will be created to identify patients with evidence of current or prior tobacco use based on diagnosis codes or pharmacy fills for smoking cessation treatments (bupropion, varenicline tartrate, or nicotine [inhalation, gum, lozenge, transdermal]).
- **Pulmonary rehabilitation**—Indicator and count variables will be created for the presence of procedure codes for pulmonary rehabilitation.

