7.6.1.3 Multivariable Analysis

Cox proportional hazards regression will be used to identify factors associated with initiation of oxygen therapy. Covariates included in the adjusted model will be determined based on statistical significance and clinical rationale. Baseline covariates may include:

- Demographic characteristics: index year, age group, gender, race/ethnicity, insurance type, geographic region
- Baseline clinical characteristics: all-cause HCRU, all-cause health care costs, medication use, respiratory disease, Quan-Charlson comorbidity score, AHRQ comorbid conditions, smoking, provider specialty, pulmonary rehabilitation

Following standard procedures, regression diagnostics will be performed for each model to assess goodness of fit and violations of model assumptions (e.g. multicollinearity, non-proportionality). Violations of the model assumptions will be documented, and appropriate corrections will be made to the analysis.

Hazard ratios and associated 95% CIs and p-values will be reported for all covariates in the model.

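### About 40% of the identification months fall in the COVID-19 pandemic, and the visible plan cannot tell oxygen started for COVID-19 from oxygen started for fibrotic ILD

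*Combined protocol and SAP*

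**What the plan says.** The data are taken "for the period of 01 October 2015 through 30 June 2022 (study period" (Section 7.1), with an option to lengthen: "The study period may be extended through latest data available at the time of study implementation to increase study sample". Within that span, the same section says that patients with "newly diagnosed fibrosing ILD will be identified from 01 October 2016 through 30 June 2022 (patient identification period".

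The rules that decide who enters and what counts as oxygen are these:

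- **Entry (Section 7.2.2).** "≥ 2 fibrosing ILD diagnoses in any position on different dates of service, within 365 days of each other". The exclusions are "Fibrosing ILD diagnosis in the 12-month pre-ILD baseline period" and unknown gender or region; the abstract adds unknown insurance type. Nothing is excluded by infectious cause.
- **Oxygen in Aim 1 (Section 7.3.1.1).** Use is captured "based on the presence of ≥ 1 diagnosis (ICD-10-CM), procedure (HCPCS, CPT), or revenue code for oxygen therapy". No limit on setting, indication or duration is given for initiation.
- **Oxygen in Aim 2 (Section 7.2.3).** A single medical claim after the ILD diagnosis places a patient in the oxygen cohort and fixes the index date.
- **Comparator index date (Sections 7.2.3 and 7.3).** It is aligned with the matched oxygen patient on time since ILD diagnosis. Calendar date is not mentioned.
- **Respiratory covariates (Section 7.3.5.2).** "pulmonary hypertension, acute respiratory failure, asthma, COPD, pneumonia, lung transplantation, upper respiratory tract infection, lower respiratory tract infection, lung cancer, and cystic fibrosis", measured in the baseline periods.
- **Calendar time.** The Aim 1 Cox model may include "index year, age group, gender, race/ethnicity, insurance type, geographic region" (Section 7.6.1.3). The abstract also lists index year as an Aim 2 baseline covariate.

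COVID-19 and the pandemic appear in none of the visible sections, including the limitations in Section 7.8, although the protocol is dated July 2023.

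**The concern.** COVID-19 pneumonia can lead to an oxygen claim and to death within a short time. A plan that identifies and follows patients through June 2022, and takes one oxygen code as initiation, will include such episodes and has no means of recognising them.

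In Aim 1, the time-to-initiation curves and the Cox model of factors associated with initiation would mix oxygen started because fibrotic disease advanced with oxygen started for an acute infection. In Aim 2, the rationale asks whether oxygen improves or worsens outcomes. A cause shared by oxygen start and early death, and not identified in the data, would confound the mortality comparison. The expected direction is against oxygen.

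**Working it through.** **1. Share of the identification period.** The plan states no month count, so there is no figure of its own to reproduce. Inputs from Section 7.1: October 2016 to June 2022. The pandemic start is not in the documents; March 2020 is assumed.

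- Identification period: 3 (2016) + 5 × 12 (2017 to 2021) + 6 (2022) = 69 months.
- March 2020 to June 2022: 10 + 12 + 6 = 28 months.
- Share: 28/69 = 40.6%.

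| Assumed start | Months to June 2022 | Share of 69 |
|---|---|---|
| January 2020 | 30 | 43.5% |
| February 2020 | 29 | 42.0% |
| March 2020 | 28 | 40.6% |
| April 2020 | 27 | 39.1% |

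A day count from 11 March 2020 gives 842/2,099 = 40.1%. The result does not depend much on the start chosen. Patients diagnosed before March 2020 are also followed into these months, so pandemic oxygen starts are not confined to patients who entered after that date.

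**2. Tracing a COVID-19 episode through the visible rules.**

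| Sequence | Aim 1 initiation | Aim 2 |
|---|---|---|
| COVID-19 and oxygen, then first ILD code within 12 months | Removed: oxygen in the pre-ILD baseline (Sections 7.3.1.1 and 7.6.1.2) | No matching exclusion in Section 7.2.3; a later oxygen claim can set the index date |
| COVID-19 before the first ILD code, first oxygen claim after it | Counts as initiation; baseline infection indicators may register the episode but not as COVID-19 | Sets the index date; same partial cover if the episode lies in the pre-index baseline |
| First ILD code, then COVID-19 and oxygen in follow-up | Counts as initiation; baseline indicators precede the episode | Sets the index date; COVID-19 first coded on that date is outside the pre-index baseline |

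The third row is the clearest gap. No visible Aim 1 variable covers it, and in Aim 2 a COVID-19 code on the index date itself is missed.

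**3. What cannot be computed.** The documents give no number of patients or oxygen starts with COVID-19, so neither the affected share nor the bias in a hazard ratio can be derived.

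**The case against.** The strongest reply is that the plan already has partial safeguards and that much of the Aim 2 method cannot be seen.

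- **Oxygen-naive restriction.** It removes from the Aim 1 initiation analysis patients whose COVID-19 oxygen came in the 12 months before the first ILD code. This stands, and it narrows the Aim 1 problem to oxygen coded on or after that date.
- **Baseline pneumonia, respiratory failure and infection indicators.** They can register an episode before the diagnosis or index date. This stands in part: they do not separate COVID-19 from other infections, and they miss what is first coded on the index date or during Aim 1 follow-up.
- **Index year.** If it enters the propensity score, some calendar alignment is achieved. But the year 2020 contains both pre-pandemic and pandemic months, and no year term identifies which patients had COVID-19.
- **Sustained use.** The requirement of at least 11 claims in 12 months filters out most short acute use. It governs neither initiation nor the Aim 2 exposure.
- **Definition.** Fibrosis that persists after an infection, coded twice, is fibrosing ILD under this plan. Keeping such patients is a choice of target population. The point here is that they cannot be identified, so the effect of that choice cannot be examined.

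A reader might go further and infer that exacerbations are contaminated too. The documents do not support that: Section 7.3.3.2 already rules out exacerbations with a pulmonary infection diagnosis in the 30 days before the CT scan.

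**Conclusion.** The concern holds as a gap that is cheap to close. Some 28 of 69 identification months (40.6%; 39.1% to 43.5% for assumed starts from April back to January 2020) fall in the pandemic, and no visible variable or analysis identifies COVID-19. Under the visible rules, oxygen given for COVID-19 on or after the first ILD code counts as initiation in Aim 1, and after that code it can set the Aim 2 index date.

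Two stronger readings should be resisted. The 40.6% is not the proportion of patients or oxygen starts affected; the documents give no basis for that figure. Nor can it be said that Aim 2 will make oxygen look harmful. Bias against oxygen in mortality is the plausible direction, but it depends on the matching variables and outcome models in Section 7.6.2, which is not shown. The code lists and table shells are not shown either, so a COVID-19 item there cannot be ruled out.

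**What to change.** 1. Add a COVID-19 diagnosis indicator to the pre-ILD and pre-index covariates, counting the diagnosis or index date itself.
2. In Aim 2, match on the calendar period of the index date (before versus from March 2020), unless the matching section already does so.
3. Pre-specify three sensitivity analyses:
   - **(a) Aim 1:** censor follow-up at the first COVID-19 claim, and exclude patients with such a claim in the 90 days up to and including the first ILD code. State that a COVID-19 claim takes precedence over an oxygen claim on the same day; otherwise same-day starts still count as events.
   - **(b) Aim 2:** exclude from both cohorts patients with a COVID-19 claim in the 90 days up to and including the index date.
   - **(c) Both aims:** end identification and follow-up on 29 February 2020.

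The 90-day window is an assumption and should be varied. Report these analyses beside the main result, state in advance what difference counts as material, and qualify the conclusion if it is reached. Add the pandemic to the limitations.

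**Cost.** One more code list, which under Section 7.7 brings extra time and fees once the protocol is approved, and re-runs of planned models. The sensitivity analyses lose precision. Analysis (c) keeps 69 − 28 = 41 of 69 identification months (59.4%) and shortens follow-up, so a difference from the main result there need not be due to COVID-19 alone. Analyses (a) and (b) should be read with it.

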7.2 SETTING

7.2.1 Secondary data source selection

The study will use administrative claims and EHR data from Optum's Market Clarity Integrated Claims + Clinical database.

7.2.2 Study population: Aim 1

The analysis for Aim 1 will include patients newly diagnosed with fibrosing ILD during the patient identification period. Patients must meet the following selection criteria to be included in the study:

Inclusion Criteria

- ≥ 2 fibrosing ILD diagnoses in any position on different dates of service, within 365 days of each other, and in the same continuous enrollment period during the patient identification period. The ***fibrosing ILD diagnosis date*** will be defined as the date of the first fibrosing ILD diagnosis. The two fibrosing ILD diagnosis codes can be one of the following combinations:
 - 2 fibrosis codes
 - 1 fibrosis code & 1 ILD code that requires fibrosis code
- ≥ 18 years of age as of the fibrosing ILD diagnosis date
- Continuous enrollment with medical and pharmacy coverage for 12 months prior to the fibrosing ILD diagnosis date (***pre-ILD baseline period***)

Exclusion Criteria

- Fibrosing ILD diagnosis in the 12-month pre-ILD baseline period
- Unknown gender or geographic region

Cohort Assignment

Patients meeting initial selection criteria for Aim 1 will be assigned to cohorts based on known cause of fibrosis:

- **IPF**— ≥ 2 medical claims with diagnosis for IPF in any position during the study period
- **Non-IPF ILD**— < 2 medical claims with diagnosis for IPF during the study period

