7.3 VARIABLES

Variables related to the study period will be defined as follows:

Aim 1

- **Fibrosing ILD diagnosis date**—The first ILD diagnosis date for patients with ≥ 2 fibrosing ILD diagnoses on different dates and within 365 days. The fibrosing ILD diagnosis date is the first day of follow-up observation time for Aim 1.
- **Pre-ILD baseline period**—The 12-month period prior to the fibrosing ILD diagnosis date.
- **Aim 1 follow-up period**—The variable period starting on the fibrosing ILD diagnosis date and continuing until the earliest of the following: disenrollment from the health plan, death, or end of the study period. The Aim 1 follow-up period will be used to assess Aim 1 outcomes.
 - **All-cause mortality**—Death will be used as a censoring event and is further defined in Section 7.3.3.1.

Aim 2

- **Index date**—For the oxygen therapy cohort, the first date following the fibrosing ILD diagnosis date with a claim with diagnosis for oxygen therapy; for the no oxygen therapy cohort, a date within the same continuous enrollment period as the fibrosing ILD diagnosis date that is similar to the matched oxygen therapy patient in time from fibrosing ILD to index date. The index date is the first day of follow-up observation time for Aim 2 and Further Aim.
- **Pre-index baseline period**—The 12-month period prior to the index date.
- **Aim 2 follow-up period**—The variable period starting on the index date until the earliest of the following: disenrollment from the health plan, death, or the end of the study period. Matched pairs will be given the same duration of follow-up. The Aim 2 follow-up period will be used to assess Aim 2 and Further Aim outcomes.
 - **All-cause mortality**—Death will be used as a censoring event and is further defined in Section 7.3.3.1.

An overview of the analytic study variables and the study periods for which each analytic variable will be reported is provided in Table 1. Additional variable information is provided in Sections 7.3.1 to 7.3.4.

Table 1. Analytic Variables by Data Source and Time Period

Characteristic	Data source		Aim 1 time period		Aim 2 time period	
	Claims*	EHR	Pre-ILD baseline	Follow-up	Pre-index baseline	Follow-up
Aim 1 outcomes						
Oxygen therapy (time to initiation, sustained oxygen therapy use)		X		X	X	
Aim 2 outcomes						
Disease progression	X	X				X
All-cause mortality	X					X
Hypoxemia	X	X	X		X	X
Acute exacerbations	X	X				X
Patient characteristics†						
Index year	X		X		X	

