7.3.5.1 Demographic Characteristics

- **Index year**—The year of the patient’s fibrosing ILD diagnosis date or index date will be identified.
- **Age**—Age will be defined as of the index year.
- **Age groups**—Patients will be assigned to one of the following age groups: 18–44, 45–64, and 65+.
- **Sex**—Sex will be captured from enrollment data; patients with undefined gender will be removed from the study sample
- **Race/ethnicity**—Patients will be classified as Hispanic, non-Hispanic White, non-Hispanic Black, non-Hispanic Asian, Other/Unknown. This variable depends on the

availability of data within the sociodemographic data and will be missing for some patients.

- **Insurance type**—Payer type will be defined as commercial, Medicare, Medicaid.
- **Geographic region**—The U.S. region in which the patient is enrolled in a health plan will be described. States will be categorized into geographic regions in accordance with the U.S. Census Bureau's region designations. The five health plan regions are presented in Table 2.

Table 2. Health Plan Regions

Region	State
Northeast	CT, MA, ME, NH, RI, VT, NJ, NY, PA
Midwest	IL, IN, MI, OH, WI, IA, KS, MN, MO, ND, NE, SD
South	DC, DE, FL, GA, MD, NC, SC, VA, WV, AL, KY, MS, TN, AR, LA, OK, TX
West	AZ, CO, ID, MT, NM, NV, UT, WY, AK, CA, HI, OR, WA
Other	Armed Forces, American Samoa, Federated State of Micronesia, Guam, Marshall Islands, Commonwealth of the Northern Mariana Islands, Puerto Rico, Palau, Virgin Islands

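### The confirming ILD code must fall before data end on 30 June 2022 while entry is dated by the first code, so index year 2022 over-represents quickly recoded patients

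*Combined protocol and SAP*

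**What the plan says.** Section 7.1 sets the study period "for the period of 01 October 2015 through 30 June 2022 (study period"), and says that patients "will be identified from 01 October 2016 through 30 June 2022 (patient identification period"). Both periods close on the same day.

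The inclusion criteria in section 7.2.2, repeated in the abstract, require at least two fibrosing ILD codes "on different dates of service, within 365 days of each other", and "in the same continuous enrollment period during the patient identification period". The first of the two codes is the diagnosis date. Section 7.3 adds: "The fibrosing ILD diagnosis date is the first day of follow-up observation time for Aim 1".

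Section 7.3.5.1 takes index year, for Aim 1, from that first code. Section 7.6.1.3 lists index year among the covariates that may enter the Cox model for oxygen initiation, and has hazard ratios, confidence intervals and p-values reported for every covariate in the model.

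Section 7.1 also allows for more data: "The study period may be extended through latest data available at the time of study implementation to increase study sample". This sentence concerns the study period and does not mention the identification period. Section 7.8 discusses misidentified and prevalent cases, but not truncation at the end of the data.

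**The concern.** The rule offers 365 days to collect the confirming code, but the full allowance exists only for first codes up to 30 June 2021. After that it shrinks by one day per calendar day, so late entrants are increasingly those whose two codes lie close together.

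A short gap plausibly marks frequent contact with care, more advanced disease, or both, and such patients may start oxygen sooner. If so, the 2022 level of index year in the Aim 1 Cox model would partly reflect the entry rule and could be read as a calendar change in prescribing. The documents give no data on how the gap relates to oxygen use, so the direction is a reasoned expectation.

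**Working it through.** **Inputs from the documents.** Identification period 1 October 2016 to 30 June 2022, which is 2,099 days; last day of data 30 June 2022; maximum gap 365 days; entry at the first code.

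**Assumed inputs.** The documents give no distribution of the gap between codes. I take first codes as evenly spread over calendar time, and gaps among patients who would be recoded within 365 days as exponential with parameter m = 45, 90 or 150 days, truncated at 365. I let patients recoded within 30 days start oxygen at k times the rate of the others, with k from 1.25 to 3. The plan states no figure on this point to reproduce.

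**Step 1: time left for the second code.** Window = min(365, days to 30 June 2022).

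- First code 30 June 2021: 365 days
- 1 July 2021: 364 days
- 1 January 2022: 180 days
- 1 June 2022: 29 days
- 30 June 2022: 0 days, so entry is impossible

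The shortened stretch is 365 of 2,099 days (17.4%). Index year 2022 is 181 days (8.6%). The other 1,734 days (82.6%) have the full window.

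**Step 2: share lost.** Loss = 1 − mean of F(r) over the days concerned, where r is the time left and F(r) = (1 − e^(−r/m)) / (1 − e^(−365/m)).

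For m = 90 and index year 2022, the mean of 1 − e^(−r/90) over r = 0 to 180 is 0.567, and the denominator is 0.983. Hence 0.567 / 0.983 = 0.577, a loss of 42.3%. The whole-cohort loss is (365 / 2,099) × the last-12-month loss, for example 0.174 × 23.0% = 4.0%.

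| Loss among otherwise qualifying patients | m = 45 | m = 90 | m = 150 |
|---|---|---|---|
| First code in last 12 months | 12% | 23% | 32% |
| Index year 2022 | 25% | 42% | 54% |
| Index year 2021 | 0.2% | 2% | 4.7% |
| Whole cohort | 2.2% | 4.0% | 5.5% |

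A wider set of gap assumptions (median 15 to 120 days, and a uniform gap) gives losses of 12% to 75% for 2022 and 1% to 9% overall.

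**Step 3: false rate ratio.** Ratio = (1 + (k − 1) × share recoded within 30 days in the group) / (1 + (k − 1) × the same share with a full window). Results at k = 2:

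| | m = 45 | m = 90 | m = 150 |
|---|---|---|---|
| Share recoded within 30 days, full window | 0.4867 | 0.2885 | 0.1987 |
| Same, 2022 entrants | 0.5967 | 0.4595 | 0.3984 |
| Ratio for 2022 | 1.5967 / 1.4867 = 1.07 | 1.4595 / 1.2885 = 1.13 | 1.3984 / 1.1987 = 1.17 |
| Ratio for 2021 | 1.001 | 1.005 | 1.008 |
| Ratio for all entrants pooled | 1.005 | 1.008 | 1.008 |

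For 2022 the ratio runs from 1.02 (k = 1.25, m = 45) to 1.29 (k = 3, m = 150). At k = 1 it is exactly 1.

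**The case against.** **The exposure in the plan is narrow.** Index year is one covariate that may enter one model, and no objective concerns calendar trend. The Aim 1 Kaplan-Meier results are stratified by IPF status, not by year. Sustained use requires 12 months after oxygen initiation, so patients first coded in the truncated year cannot contribute to it under the current dates. All of this stands, and it is why the point matters for the 2022 estimate and little else.

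**The size is assumed.** This also stands. The gap distribution, the 30-day cut and k are all mine. The shrinking window, however, follows from the dates alone.

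**The wording could be read differently.** The identification-period phrase might govern the enrollment span or the first code only. That does not help, because no code after 30 June 2022 is in the data.

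**The extension might solve it.** It does not as written. If only the study period moves, 7.2.2 still confines the codes to the identification period. If both end dates move together, the truncation moves to the new end date.

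**Three stronger readings are tempting and not supported.**

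- A reader might infer that 2021 is distorted too. A July 2021 first code still has almost the full year, and the false ratio for 2021 is at most 1.008 at k = 2.
- A reader might infer that early initiation estimates are pushed up. The pooled shift is under 1% at k = 2, which is negligible.
- A reader might infer that the bias remains wherever follow-up starts. It does not. If entry and index year were dated by the confirming code, simulation with the same gaps gives shares recoded within 30 days of 0.487, 0.288 and 0.197 in the last 181 days, against 0.486, 0.289 and 0.199 mid-study. The distortion comes from dating entry by the first code.

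**Conclusion.** The point holds in limited form. As written, the entry rule selects on a short gap between codes, with a strength that grows from July 2021 and matters mainly in index year 2022. Under exponential gaps with mean parameter 45 to 150 days, about 25% to 54% of otherwise qualifying 2022 patients are lost. The 2022 oxygen-initiation rate is inflated by a factor of about 1.02 to 1.29 if quickly recoded patients start oxygen at 1.25 to 3 times the rate of the others.

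The mechanism rests on the stated dates. The sizes rest on assumptions that the documents neither support nor contradict. The pooled Aim 1 results are not seriously threatened. A 2022 hazard ratio from the Cox model should not be taken at face value.

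**What to change.** In section 7.2.2, apply the identification period to the first code only, and let the confirming code fall up to 365 days later within the study period. This wording has an effect only if the data run beyond the last permitted first code.

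- **If data are extended under section 7.1:** end the first-code window 365 days before the new last data date, so that every entrant has the same 365 days. The cost is fewer added entrants than the extension could otherwise bring. Keeping first codes to 30 June 2022 needs data to 30 June 2023. Extraction is planned for August 2023, but the documents do not say how far the data will then reach.
- **If data are not extended:** keep the main cohort, repeat the Aim 1 Kaplan-Meier and Cox analyses with first codes limited to 30 June 2021 (1,734 of 2,099 entry days), and do not interpret the 2022 index-year hazard ratio from the unrestricted model. The cost is one extra analysis. Dropping 17% of entry days from the main analysis would be a debatable trade for a pooled shift this small.
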